#### 4.6 Other analyses

#### 4.6.1 Other variables and/or parameters

Not applicable.

#### 4.6.2 Subgroup analyses

Subgroup analyses are performed to evaluate the consistency of the primary efficacy result across different relevant subgroups. Subgroup analyses of the rate of clinically relevant asthma exacerbations during the efficacy evaluation period (period 4) include:

- age group at randomisation (5-11,12-17 years)
- sex
- race (caucasian, non-caucasian)

Type of document	Date:	11-Aug-2022	
Document ID	Version:	4.0	
	Status:	Final	
INTERNAL USE	Page:	41 of 79	•••••

- asthma background treatment (ICS, ICS plus LABA)
- allergen sensitivity (HDM only, HDM + others)
- geographic region (US, Europe)

The trial is not powered to detect a treatment effect within a subgroup and the subgroup analyses will thus only be descriptive in nature.

A forest plot will be provided by the above specified subgroups. The plot will display the estimated ratio of rates to placebo (and corresponding confidence interval) for each subgroup. The same NB regression model as in the primary efficacy analysis will be applied for the subgroup analyses based on all observed data in FAS corresponding to the primary estimand. The subgroup analyses will be performed using the statistical model for the primary analysis with the inclusion of the subgroup analysed and an interaction with treatment.

# 4.7 Interim analysis

No interim analysis will be performed.

# 4.8 Changes to the protocol-planned analyses

Changes to the protocol are described in this section.

#### Impact of Covid-19

- Due to the Covid-19 pandemic that has impacted the MT-11 trial from Q1 2020, it has been decided not to perform the planned 2nd blinded sample size reassessment (SSR) with a data cut-off point closest to but not before 1st of March 2021.
- As a consequence of the ongoing Covid-19 pandemic, it has been decided to analyse the impact of Covid-19 on the primary and key secondary endpoints by repeating the analyses including an Covid-19 effect on two levels: before and during Covid-19.
- The end of trial date has been changed to be the date of the sponsor's decision to end the trial, due to the trial's severe impact by the Covid-19 pandemic. This date was 10th of August 2022.

#### AEs

- The list of PTs defining the solicited AEs has been expanded.
- Treatment-emergent AEs (TEAEs) have been redefined to exclude AEs with a start day more than 7 days after last IMP administration. In addition, the term non-TEAE has been introduced and specified.

#### Statistical models

- The model for the key secondary endpoints "proportion of days with nocturnal awakening which require SABA" is changed from a generalized linear mixed effect model to a marginal logistic regression model estimated by a GEE approach. GEE estimation has fewer model assumptions and hence reduces the risk of wrong model assumption. In addition, the treatment effect has an interpretation as a population average estimate in the GEE approach.
- All MMRM analyses have been aligned and updated to include the following fixed factors: treatment, visit, treatment-by-visit interaction, age group and region. Baseline values at visit

Type of document	Date:	11-Aug-2022	
Document ID	Version:	4.0	
	Status:	Final	
INTERNAL USE	Page:	42 of 79	

3 will be included as a covariate. The default within-subject correlation structure has been changed from a Toeplitz covariance to an unstructured covariance.

The model for the 2 additional secondary endpoints "Time to first severe asthma exacerbation" and "Time to first clinically relevant asthma exacerbation" has been changed to a Cox proportional hazards regression analysis including treatment and age group (<12 years/≥ 12 years) as effects. Region is included as a random effect assumed to follow a gamma distribution.

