The proportion of days with nocturnal awakening which require SABA use over the two weeks diary assessment period (before V5, V6, V7, V8, V9, V10 and V11) will be analysed by means of a generalised linear mixed effect model (GLMM) with a logit link function. Treatment, visit, age group (<12 years/≥ 12 years) and country will be included as fixed factors. Baseline proportions of nocturnal awakenings requiring SABA will be included as a covariates and subject will be included as a random effect. Parameters in the model are estimated by applying pseudo-likelihood techniques as in Wolfinger and O'Connell (Wolfinger & O'connell 1993) and Breslow and Clayton (Breslow & Clayton 1993). From the GLMM model, the odds ratio for having a day with nocturnal awakening of active treatment relative to placebo will be presented together with the coherent p-values and 95% confidence limits.

The average daily dose of SABA over the two weeks diary assessment period (before V5, V6, V7, V8, V9, V10 and V11) will be analysed by means of a mixed-effect model repeated measurement (MMRM). The model includes treatment, visit, age group (<12 years)≥ 12 years) and country as fixed factors, the baseline average daily SABA dose as a covariate and subject as a random effect. Different residual errors for each treatment group will be speficied and the within-subject correlated errors is modelled with a Toeplitz structure (TOEP). A between treatment comparison will be performed by means of a t-test with Kenward-Roger degrees of freedom approximation. The resulting p-value will be reported together with the difference in adjusted means. In addition the relative difference will be reported together with 95% confidence limits calculated based on Fieller's theorem.

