### 4.3 Secondary endpoint analyses

For all secondary endpoints (key secondary and additional secondary endpoints), no data collected after treatment discontinuation is used.

Type of document Document ID	Date: Version: Status:	11-Aug-2022 4.0 Final	ALK
INTERNAL USE	Page:	32 of 79	

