### 4.3.1.3 Main analytical approach

The key secondary endpoints will be compared between treatment groups using the primary estimand for the FAS population.

The proportion of days with nocturnal awakening which require SABA rescue medication over the 14 days eDiary assessment period (before V5, V6, V7, V8, V9, V10 and V11) will be modelled by a marginal logistic regression model with an unstructured working covariance matrix. The response variable is the number of days with nocturnal awakenings due to asthma requiring SABA rescue medication out of the total number of days recorded. Treatment, visit and treatment-by-visit interaction, age group (<12 years/≥ 12 years) and region will be included as fixed effects. Baseline proportions of nocturnal awakenings requiring SABA will be included as a covariate. The marginal model will be estimated using a generalized estimating equations (GEE) approach. The treatment effect on the logit scale is an average treatment effect across all visits and will be estimated as a contrast of parameters in the marginal model. For both the overall treatment effect and the effect per visit, the corresponding odds ratio for proportions of days with nocturnal awakening requiring SABA of active treatment relative to placebo will be presented together with the coherent p-value and 95% confidence limit.

The proportion of days with SABA use over the 14 days eDiary assessment period (before V5, V6, V7, V8, V9, V10 and V11) will be analysed by means of a marginal logistic regression model and a GEE estimation approach as described for "proportion of days with nocturnal awakening which require SABA".

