#### Endpoints

- A new additional secondary endpoint has been added: "Change from baseline in percentage predicted FEV1".
- The key secondary endpoint for SABA use has been changed from a continuous endpoint (average daily doses) to a binary endpoint (proportion of days). The reason is that many subjects do not use any SABA and the resulting excessive number of zeros are challenging to model as a continuous variable. The continuous endpoint "Average daily dose of SABA" will instead be analysed as an additional secondary endpoint.
- Explorative endpoints have been renamed to Other endpoints.

- If any subject exceeds the recommended daily dose of a symptomatic medication for rhinitis or rhinoconjunctivitis, the maximal daily score will be used and not the actual score as specified in the protocol.
- Additional description of how safety endpoints are summarised are added:
  - Duration in minutes of the solicited AEs occurring on first day of IMP intake, treatment-emergent anaphylactic reactions, anaphylaxis and/or systemic allergic reactions, TEAEs treated with adrenaline/epinephrine, treatment-emergent severe local swelling or oedema of the mouth and/or throat, treatment-emergent eosinophilic oesophagitis, medication error, local application site TEAEs, onset and resolution time in days for most frequent TEAEs (≥2% of subjects in active group), onset and resolution time in days for local application site TEAEs, drug abuse, misuse and overdose.

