#### 7.2.3 Secondary endpoints analysis

In the analysis of the first and second key secondary endpoints, the marginal model will be estimated using a GEE- approach. The treatment effect on the logit scale is an average treatment effect across all visits and will be estimated as a contrast of parameters in the marginal model. The corresponding odds ratio for proportions of days with nocturnal awakening requiring SABA of active treatment relative to placebo will be presented together with the coherent p-value and 95% confidence limit. If convergence issues are encountered for the marginal logistic regression model, other working covariance structures will be considered (e.g. an independence structure (IND)).

In the analysis of the third key secondary endpoint and the additional secondary endpoints, the treatment effect is the average of the treatment effect across all visits and will be estimated as a contrast of the parameter estimates in the MMRM model. The corresponding p-value will be calculated by means of a t-test with Kenward-Roger degrees of freedom approximation. LSMeans by treatment group will be displayed. In addition, the relative difference will be reported together with 95% confidence limits calculated based on Fieller's theorem for non-transformed data. In models where data is square-root transformed, the absolute difference will be calculated based on a second-order Taylor series expansion.

If an MMRM model with an unstructured covariance matrix fails to converge, unstructured correlations (UNR), Toeplitz (Toep) or compound symmetry (CS) will be used instead, prioritized in the listed order. If the MMRM model still fails to converge, a reduced model is used to estimate starting values for the type of covariance structure mentioned above. If the use of starting values will still not lead to convergence, the model is reduced by eliminating effects backwards (i.e. first region then age group).

If a Cox proportional hazards regression models fails to converge in the analysis of time to events, e.g. due to few events, then Firth's penalized maximum likelihood estimation is used.

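### Key secondary tests 1 and 2 now rest on unweighted GEE: the bias is small with the planned unstructured matrix but clearly larger with the independence fallback, and no missing-data sensitivity analysis is planned

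*SAP*

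**What the plan says.** **Key secondary 1, nocturnal awakenings.** In Protocol 15.8 the endpoint "will be analysed by means of a generalised linear mixed effect model (GLMM) with a logit link function", with subject as a random effect. On the fitting method it says: "Parameters in the model are estimated by applying pseudo-likelihood techniques". In SAP 4.3.1.3 the same endpoint "will be modelled by a marginal logistic regression model with an unstructured working covariance matrix", estimated by GEE. SAP 4.8 gives two reasons: "GEE estimation has fewer model assumptions and hence reduces the risk of wrong model assumption", and a population-average interpretation of the treatment effect.

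**Key secondary 2, SABA.** Protocol 15.8 planned an MMRM on average daily dose. SAP 4.8 replaces the endpoint itself: "The key secondary endpoint for SABA use has been changed from a continuous endpoint (average daily doses) to a binary endpoint (proportion of days". The stated reason is the excess of zeros. SAP 4.3.1.3 then applies the same GEE approach.

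**Missing data.** SAP 4.3 states: "For all secondary endpoints (key secondary and additional secondary endpoints), no data collected after treatment discontinuation is used". SAP 4.3.1.4 and 4.3.1.5 list no sensitivity or supplementary analyses. The Covid-19 repeats in 4.3.1.6 leave the missing-data assumption unchanged.

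**Fallback.** If the logistic model does not converge, SAP 7.2.3 says "other working covariance structures will be considered (e.g. an independence structure (IND", with no order. For the MMRM, the same section gives an ordered list.

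**The concern.** Both endpoints moved from a likelihood-type mixed model to estimating equations without weights. Ordinary GEE is in general consistent only if missingness is completely at random (MCAR) or depends on covariates in the model. A likelihood fit of a correct model needs only MAR, so missingness may also depend on earlier observed outcomes.

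Some missingness here plausibly does. Protocol 5.1 requires treatment to stop after two severe exacerbations in 12 consecutive months, or after an asthma hospitalisation that needs systemic corticosteroids. Protocol 5.2 lists perceived lack of effect as a reason to withdraw. When worse subjects leave, those who remain look better, more so on placebo if the tablet works. The averaged odds ratio then moves towards 1.

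The SAP is uneven on this point. For the primary endpoint, 4.2.3 names the MCAR assumption and 4.2.4 plans two sensitivity analyses. Section 1.1.9.7 handles discontinuations for the key secondary endpoints in the same way, but these endpoints get no sensitivity analysis. At stake is power at hypotheses 2 and 3, and at FEV1 behind them, since a failed step ends the hierarchy (SAP 2.1).

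**Working it through.** The documents give no power or bias figure for these tests, so there is none to reproduce. The check was a reading of the models side by side, followed by simulation.

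**Inputs from the documents.** Seven diary periods (V5 to V11) of 14 days each; GEE with an unstructured working matrix, independence as the named fallback; 30% dropout for all reasons assumed in planning (Protocol 15.1). Prevalence, correlation, treatment effect and dropout mechanism are not given and were assumed.

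**Measure.** Share of the log odds ratio lost = ln(OR with dropout / OR without dropout) / |ln(OR without dropout)|.

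**Simulation A.** 200,000 subjects per scenario, with MAR dropout that depends on the last diary proportion, 24-47% in total. Unstructured lost 3-10%; for example OR 0.671 became 0.697, and ln(0.697/0.671)/|ln 0.671| = 0.038/0.399 = 9.5%. Independence lost 9-25%; 0.671 became 0.742, or 0.101/0.399 = 25%. Weighted GEE recovered the full-data value within about 3% on the log scale in three of four scenarios and over-corrected in the one with heaviest dropout.

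**Simulation B.** Six runs of 16,000 subjects, 13-34% dropout by the last visit. Entries are ratios of the OR with dropout to the OR without.

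| Outcome-driven dropout | Full-data OR | Unstructured (loss) | Independence (loss) |
|---|---|---|---|
| Both arms, random intercept | 0.740 | 1.011 (3.6%) | 1.040 (13%) |
| Both arms, plus visit-level correlation | 0.764 | 1.018 (6.6%) | 1.038 (14%) |
| Placebo only, random intercept | 0.754 | 1.025 (8.7%) | 1.235 (75%) |
| Placebo only, plus visit-level correlation | 0.770 | 1.028 (11%) | 1.259 (88%) |
| Both arms, no true effect | 0.986 and 0.995 | 0.999 and 1.000 | 0.994 and 1.000 |

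Example, first row: ln 1.011/|ln 0.740| = 0.0109/0.301 = 3.6%. Exchangeable gave 1.009 and 1.016 in the first two rows, about as good as unstructured. MCAR dropout gave 0.995-1.001 throughout, and dropout driven by latent severity gave 0.98-1.00. A maximum-likelihood random-intercept logit gave 1.00, run only in the random-intercept setting. The protocol's pseudo-likelihood fit was not evaluated.

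**Simulation C.** 33-65% dropout. Unstructured lost 1-5%, exchangeable 1-5%, independence 8-19% (57% with outcome-driven dropout on placebo only).

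**Range for dropout in both arms.** Unstructured about 1-10%, independence about 8-25%.

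**The case against.** Much can be said for the plan, and most of it stands.

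- A reader might infer that both tests left a GLMM that was valid under MAR. They did not. SABA was an MMRM on a different, continuous endpoint, and the rationale quoted from SAP 4.8 concerns nocturnal awakenings only. The GLMM was a pseudo-likelihood fit, so its MAR validity is approximate. The exacerbations that trigger stopping are not in that model. The protocol claims MAR only for the primary negative binomial model (15.13).
- A reader might infer that dropout is driven by asthma outcomes. The documents show only that part of it is. Protocol 5.1 also lists oesophagitis symptoms, pregnancy and investigator opinion, and no counts by reason are given. Protocol Table 14 shows early loss in cohorts 1 and 2 of (325 - 316)/325 = 2.8%.
- The two-exacerbation rule may bite rarely. SAP 5.1 reports 81% power at 900 subjects. Put into the formula in Protocol 15.2.1 with RR 0.7, and assuming k = 0.7, 608 days and 3% early loss: (0.878 + 1.960)²/(ln(1/0.7))² = 63.3; 450 × 0.97/63.3 = 6.90; 6.90 - 1.40 = 5.50; rate = 2.89/(1.4 × 5.50 × 608/365) = 0.23 per year. With 500-608 days and 3-10% early loss the range is 0.23-0.30, and the chance of two or more exacerbations of any kind in a year is about 3-5% (1-23% for k from 0 to 2.5). The hospitalisation rule is not covered.
- Little is discarded by rule: SAP 1.1.9.3 says only 3 subjects stopped treatment without leaving the trial at that time. Equally, off-treatment data cannot fill the gap.
- The change of model did not create the lack of sensitivity analyses. Protocol 15.13 planned them for the primary endpoint only.
- SAP 4.8 is right about random-effect and distributional assumptions, and a population-average effect is a legitimate aim.

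What survives is the unstated missing-data assumption, the open-ended fallback and the missing sensitivity analysis.

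**Conclusion.** The point holds in a limited form. Hypotheses 2 and 3 rest on unweighted GEE, whose missing-data assumption is stronger than SAP 4.8 implies and is never varied. With the planned unstructured matrix the expected attenuation is small, about 1-10% of the log odds ratio. The independence fallback is the sharper problem, at about 8-25%, and 57-88% in the extreme case of outcome-driven dropout on placebo only.

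These sizes rest on assumed prevalence, correlation and dropout, some of it heavier than the planned 30%. The direction is the firmer result.

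A reader might infer a risk of false positive findings. The simulations do not support that: with no true effect and the same mechanism in both arms, the ratios were 0.99-1.00. With no true effect and outcome-driven dropout on placebo only, independence gave 1.24-1.25, an error against the tablet. Outcome-driven dropout confined to the active arm was not simulated and would reverse that sign. The documents give no discontinuation pattern by arm, so neither one-sided case should be taken as expected.

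**What to change.** 1. **SAP 7.2.3.** Replace the open-ended fallback with an ordered list of correlated structures, for example Toeplitz and then exchangeable. Allow independence only with inverse-probability weights. Exchangeable did about as well as unstructured in the simulations; Toeplitz was not simulated.
2. **SAP 4.3.1.4.** Add one MAR-based sensitivity analysis for both endpoints. This can be weighted GEE, with the probability of remaining on treatment modelled from treatment, last diary proportion, exacerbations to date, age group and region, or multiple imputation.
3. **SAP 4.8.** Say that GEE makes fewer distributional assumptions but a stronger missing-data assumption.

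The unstructured GEE may stay as the main analysis. The cost is SAP wording and modest programming, plus somewhat larger variance in a weighted analysis. Weighted GEE over-corrected in one simulated scenario, and simulations of this size say nothing about weight stability with 533 randomised subjects. It is therefore better placed as a sensitivity analysis than as the main test.

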#### Endpoints

- A new additional secondary endpoint has been added: "Change from baseline in percentage predicted FEV1".
- The key secondary endpoint for SABA use has been changed from a continuous endpoint (average daily doses) to a binary endpoint (proportion of days). The reason is that many subjects do not use any SABA and the resulting excessive number of zeros are challenging to model as a continuous variable. The continuous endpoint "Average daily dose of SABA" will instead be analysed as an additional secondary endpoint.
- Explorative endpoints have been renamed to Other endpoints.

- If any subject exceeds the recommended daily dose of a symptomatic medication for rhinitis or rhinoconjunctivitis, the maximal daily score will be used and not the actual score as specified in the protocol.
- Additional description of how safety endpoints are summarised are added:
  - Duration in minutes of the solicited AEs occurring on first day of IMP intake, treatment-emergent anaphylactic reactions, anaphylaxis and/or systemic allergic reactions, TEAEs treated with adrenaline/epinephrine, treatment-emergent severe local swelling or oedema of the mouth and/or throat, treatment-emergent eosinophilic oesophagitis, medication error, local application site TEAEs, onset and resolution time in days for most frequent TEAEs (≥2% of subjects in active group), onset and resolution time in days for local application site TEAEs, drug abuse, misuse and overdose.

# 5 SAMPLE SIZE DETERMINATION

The primary endpoint is the annualised rate of clinically relevant asthma exacerbations during the efficacy evaluation period (period 4). The rate of clinically relevant asthma exacerbations will be analysed using a negative binomial regression model.

From (Lanier et al. 2009) the rate of clinically relevant asthma exacerbations is expected to be approximately 1.4 exacerbations per subject per year. Over a period of 24 weeks, the number of clinically relevant asthma exacerbation in the placebo group were 0.64 per subject ( $\sim$ 0.64\*52/24 = 1.4 per subject per year).

Power calculation are both performed based on the negative binomial distribution assuming overdispersion and based on the Poisson distribution when assuming no overdispersion. Overdispersion means that some subjects will tend to have more exacerbations than others. The dispersion parameter in the negative binominal distribution is assumed to be k=0.7 (**Pavord et al.**)

Type of document Document ID	Date: Version: Status:	11-Aug-2022 4.0 Final	
INTERNAL USE	Page:	43 of 79	

**2012)**. When there is no overdispersion  $(k \rightarrow 0)$  the negative binominal distribution will become a Poisson distribution.

**Table 5** displays the sample size calculations for different values of the treatment effect expressed as the reduction in exacerbation rates for active treatment compared to placebo (100%\*(PLB-ACT/PLB)). The power is set to 90% and sample size calculations are performed using a close formula for the negative binomial regression model (Keene et al. 2007):

$$N = \left\{ \frac{z_{1-\beta} + z_{1-\alpha/2}}{\log(\mu_1/\mu_2)} \right\}^2 \times \left\{ \frac{\mu_1 + \mu_2}{\mu_1\mu_2} + 2k \right\}$$

where N is the number of subjects per treatment arm,  $\mu_1$  is the rate per subject in the given time interval for the placebo group,  $\mu_2$  is the rate per subject in the given time interval for the active group,  $1 - \beta$  is the power, alpha is the level of significance and k is the dispersion parameter.

Power	Alpha	Time for efficacy assessment (weeks)	Rate PLB	Reduction (%) 100%*(PLB- ACT)/PLB)	μ 1	μ2	k	N per arm (NB*)	N per arm (POIS)
	0.05	34			0.91	0.63		334	219
	0.05	52		30%	1.39	0.97		259	143
	0.05	86			2.29	1.61		202	87
	0.05	34			0.91	0.68		501	324
0.9	0.05	52	1.4	25%	1.39	1.04	0.7	389	212
	0.05	86			2.29	1.72		306	128
	0.05	34			0.91	0.73		814	519
	0.05	52		20%	1.39	1.11		635	339
	0.05	86			2.29	1.83		500	205

Table 5Power calculation

PLB: placebo, ACT: active, NB: negative binominal, POIS: Poisson distribution.

If assuming a drop-out rate of 30%, a power of at least 90% and an efficacy assessment period of 20 months (86 weeks), a sample size of approximately 300 ( $\sim$ 205/0.7=293) subjects per arm should be sufficient to detect a difference in exacerbation rates of 20% when no overdispersion is present as shown in **Table 5**. In case of overdispersion defined by a dispersion parameter of k=0.7, a sample size of 300 (>202/0.7=288) subjects per arm would be sufficient to detect a difference in the exacerbation rates of 30%.

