### 1.2 Trial design

This trial is a randomised, parallel-group, double-blind, placebo-controlled, multi-national phase III trial conducted in Europe and North America.

The trial was initiated in Q1 2018 and subjects were to receive treatment for 24-30 months consisting of a treatment initiation and maintenance period of 4-10 months followed by a 20-month efficacy assessment period.

A total of 533 subjects were randomised to receive treatment with the HDM SLIT-tablet or placebo, see **Figure 1**.

Type of document Document ID	Date: Version: Status:	11-Aug-2022 4.0 Final	
INTERNAL USE	Page:	20 of 79	

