#### 12 SQ-HDM, 300 subjects N = 600 Placebo, 300 subjects Period 3 Period 2 Treatment Period 4 Period 1 initiation and Screening 3 weeks Baseline; Efficacy assessment period; maintenance; 20 months 4-10 months Screening visit Randomisation Baseline visit End of trial visit Å Solicited /isit /isit ٧9 ٧1 V2 V4 V6 ٧7 ٧8 V10 V11 V3 ٧5 3 weeks 4 weeks 3 months 4 months 4 months 4 months 4 months 4 months

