OP1	• The time period is from the start of the trial and until March 20, 2020, both dates included
OP2	• The time period is from March 20, 2020 (excluded) until the end of the trial

### 3.1 Issue at site 613

In Sep-2018 the CRO discovered that 2 subjects at the site had been enrolled in 2 different trials for 2 different sponsors at the same time. Evaluation from the CRO medical monitor review showed that subjects' safety was not affected. All 9 subjects at the site were discontinued from the trial in Nov-2018 and the site was terminated in Mar-2019.

Thus, efficacy data from site 613 are neither included in the PP, nor in the FAS. However, safety data from site 613 are included in the SAF.

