# 5.1 Sample size reassessment

A blinded sample size reassessment (SSR) has been performed according to the protocol section 15.2.1. For each subject, the data cut-off-point for the SSR was the visit (including TCs) closest to but not before the 1st of February 2020.

Type of document	Date:	11-Aug-2022	
Document ID	Version:	4.0	
INTERNAL USE	Status: Page:	Final 44 of 79	

The conclusion of the SSR was that the reassessed sample size is 900 subjects, corresponding to a power of 81%. However, it was decided not to recruit for a new cohort as it was assessed that the SSR may not be accurate as the exacerbation rate was uncertain due to a very limited number of observations and due to the fact that the Covid-19 situation with rules of social distancing was likely to reduce transmission of respiratory infections, and thus also the number of exacerbations.

It was decided to perform a new SSR based on data sets from Cohort 1-3, however the SSR was not performed. Details are provided in section **4.8**.

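### SAP section 5 and Figure 1 still show 90% power at 300 per arm, while the SAP's only completed reassessment implies about 58% for the at most 524 subjects in the FAS, a figure the SAP does not give

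*SAP*

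**What the plan says.** SAP section 5 repeats the protocol's calculation. With a placebo rate of about 1.4 per subject-year, dispersion k = 0.7, 86 weeks of efficacy assessment, 30% drop-out and 90% power, it concludes that "a sample size of 300 (>202/0.7=288) subjects per arm would be sufficient to detect a difference in the exacerbation rates of 30" per cent. Figure 1 in SAP section 1.2 shows "12 SQ-HDM, 300 subjects N = 600 Placebo, 300 subjects".

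The same SAP, dated 11 August 2022, gives different numbers for the trial that was run:

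- Section 1.2: "A total of 533 subjects were randomised".
- Section 3.1, on site 613: "All 9 subjects at the site were discontinued from the trial", and "efficacy data from site 613 are neither included in the PP, nor in the FAS".
- Section 5.1, on the first blinded SSR: "The conclusion of the SSR was that the reassessed sample size is 900 subjects, corresponding to a power of 81" per cent.
- Section 5.1, on why no cohort was added: "it was assessed that the SSR may not be accurate as the exacerbation rate was uncertain due to a very limited number of observations". It adds that social distancing was likely to reduce exacerbations.
- Section 5.1, on the second SSR: "It was decided to perform a new SSR based on data sets from Cohort 1-3, however the SSR was not performed".

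Protocol section 15.2.1 fixes the SSR effect at a rate ratio of 0.70 and caps the trial at 900 randomised subjects.

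**The concern.** A reader of section 5 finds 90% power at 300 per arm and then, in 5.1, 81% at 450 per arm. Neither size was reached. For the roughly 262 per arm who can enter the FAS, the SAP gives no power at all. Yet the pair reported in 5.1 is enough to work it out, and the answer is far from 90%.

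This bears mainly on how a null result would be described. On the SSR's estimates, a true 30% reduction would be missed about 42% of the time. A non-significant primary test also stops formal testing of the three key secondary endpoints (SAP section 2.1). If the report carries forward only the 90% figure, a non-significant result could be taken as stronger evidence of no effect than the sponsor's own reassessment supports.

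**Working it through.** **1. The plan's own figure.** The formula in SAP section 5 is N per arm = {(z_power + z_0.975)/ln(μ1/μ2)}² × {(μ1 + μ2)/(μ1μ2) + 2k}.

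- μ1 = 0.64 × 86/24 = 2.293; μ2 = 0.7 × 2.293 = 1.605; k = 0.7.
- Second bracket: 3.899/3.681 + 1.4 = 2.459.
- First bracket squared: (1.282 + 1.960)²/0.1272 = 82.6.
- N = 82.6 × 2.459 ≈ 203 per arm, against 202 stated. Using 1.4 × 86/52 for μ1 gives 202.3.
- 202/0.7 = 288.6, rounded up to 300 per arm.

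The planning sentence is therefore correct on its inputs. All 18 sample sizes in Table 5 also reproduce within 3%.

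**2. Subjects available.** 533 − 9 = 524. Protocol Table 14 gives the same total with site 613 excluded: 76 + 249 + 199 = 524. This is an upper bound, because the FAS also requires at least one dose.

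**3. Scaling the SSR.** In the protocol 15.2.1 formula, the blinded rate, the dispersion, the mean time in period 4 and the drop-out before period 4 form one constant that multiplies (z_power + z_0.975)². At a fixed rate ratio, N is therefore proportional to (z_power + z_0.975)², and

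power(N) = Φ[(z_0.81 + 1.960) × √(N/900) − 1.960], with z_0.81 + 1.960 = 0.878 + 1.960 = 2.838.

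The formula divides by (1 − drop-out), so N counts randomised subjects, and 524 and 533 are on the right scale.

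| Subjects | √(N/900) | × 2.838 | − 1.960 | Power at rate ratio 0.70 |
|---|---|---|---|---|
| 524 | 0.763 | 2.165 | 0.205 | 58.1% |
| 533 | 0.770 | 2.184 | 0.224 | 58.9% |
| 600 | 0.816 | 2.317 | 0.357 | 64.0% |
| 900 | 1.000 | 2.838 | 0.878 | 81% (stated) |

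The SSR's individual estimates are not published, but they cancel. Twelve combinations of rate, dispersion, time and drop-out chosen to give 81% at 900 all returned 58.1% at 524 and 58.9% at 533. If 81% is itself rounded (80.5% to 81.5%), the 524 figure lies between 57.6% and 58.7%.

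**4. Sensitivity to the SSR being wrong (assumption: variance term off by 25%).** Power at 524 = Φ[2.165/√f − 1.960], where f is the true variance divided by the SSR's variance.

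- f = 0.75 (SSR too high): Φ(0.540) = 71%.
- f = 1.25 (SSR too low): Φ(−0.023) = 49%.

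**5. Detectable effect at 524 on the SSR's estimates.** The implied variance per randomised subject is 450 × 0.1272/2.838² = 7.11, so SE(log rate ratio) = √(7.11/262) = 0.165. The reduction detectable with 80% power is 1 − exp(−2.802 × 0.165) = 37%; with 90% power it is 1 − exp(−3.242 × 0.165) = 41%. Both hold the variance at its value for a rate ratio of 0.70.

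**The case against.** The case on the other side is substantial, and several parts of it stand.

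- **No arithmetic error.** This is right. Section 5 reproduces, and its language is that of a planning assumption.
- **Already disclosed.** Section 5.1 follows directly and reports the SSR, the doubts, the decision not to recruit and the dropped second SSR. That stands too: a careful reader would realise that 90% cannot hold at 533 if 900 gives 81%. But such a reader must still derive the figure, and nothing marks section 5 or Figure 1 as superseded.
- **The SSR is distrusted.** It rested on few observations, stopped at about February 2020, took mean follow-up from cohort 1 only, and assumed no discontinuation after about 17 months. This limits what 58% can mean, and is why a range belongs beside it. Two of these points suggest that 58% is not pessimistic: the discontinuation assumption favours power, and a Covid-related fall in exacerbations would reduce it.
- **The confidence interval already answers the question.** The rate ratio is reported with a 95% interval, which shows directly which reductions a null result leaves open. This stands, and the fix should point readers to it.

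A reader might infer three stronger things that the documents do not support. The first is that the true power was 58%: that figure is only what the sponsor's 900/81% pair implies. The second is that the SSR result was concealed, which section 5.1 plainly refutes.

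The third is that the loss of power can be split neatly between fewer subjects and worse estimates, by taking 87–88% as the planning-input power at the achieved size. That figure treats the 30% planning drop-out as total loss: 262 × 0.7 = 183.4 evaluable per arm gives 87%. Protocol Table 14 shows 72 of 76 and 244 of 249 subjects entering period 4, a loss of 9/325, about 3%. With that loss and full follow-up, 262 × 0.972 = 254.7 per arm gives about 95% on the planning rate and dispersion. That is an upper-side illustration, since partial follow-up lowers it. The comparator depends too heavily on the drop-out convention to be used without that qualification.

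**Conclusion.** The point holds as a gap in reporting. A SAP finalised after recruitment presents a power and a sample size that do not describe the trial as run, and omits the figure its own reassessment implies: about 58% at 524 subjects, 59% at 533 and 64% at the planned 600, for a rate ratio of 0.70.

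Confidence is high in the scaling. It rests on the SAP's 900/81% pair, the protocol's formula, 1:1 allocation, and the SSR's drop-out and mean follow-up applying to the achieved sample. Confidence is much lower in 58% as the actual power; 49% to 71% is the range under an assumed 25% error in the variance term. The correction is worth making because it is cheap, but it affects interpretation only. No estimand, test or estimate is in question.

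**What to change.** Label section 5, Table 5 and N = 600 in Figure 1 as the original planning calculation. Add to section 5.1:

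> On the first blinded SSR's estimates, power for RR = 0.70 is about 58% with 524 subjects (59% with 533 randomised; 64% with the planned 600). These estimates rest on few observations; if the variance term were 25% too high or too low (an assumption), power at 524 would be about 71% or 49%. A COVID-related fall in the exacerbation rate, other inputs unchanged, would lower it further. The 90% planning power does not apply to the achieved sample size; a non-significant result should be read from the 95% CI of the rate ratio.

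Leave out the 87–88% planning-input comparator, or state that it treats the 30% drop-out as total loss. Carry the same wording into the trial report.

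The cost is a few sentences and a figure label. Enrolment and analyses are unchanged. The drawback for the sponsor is that the stated power becomes less favourable.
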